3.7.1.8 Double-blind Randomized Withdrawal Phase Week 12 or Early Termination

One day before the Week 12 (\pm 3 days) visit of the double-blind randomized withdrawal phase, subjects will take their final dose of double-blind IMP. The subject will return to the clinic for the final trial visit at the double-blind randomized withdrawal phase Week 12 visit. If the subject terminates early from the trial, the end-of-treatment visit procedures should be completed. For subjects who discontinue early, attempts should be made to complete ALL evaluations, particularly efficacy assessments (YGTSS, CGI, etc.), for the Week 12/ET visit prior to the administration of any new psychotropic medications. However, if the subject receives a new psychotropic medication prior to ET procedures, no efficacy assessments should be done. Any prohibited medications started before the end of the trial assessments should be documented as a protocol deviation in the source notes.

The following procedures are to be completed:

- 1) Current psychotropic therapy will be recorded.
- 2) The YGTSS and CGI-TS (both the severity and improvement scales) will be performed to assess symptoms associated with TD.
- 3) Completion of the C-SSRS (children's version).
- 4) The SAS, BARS, and AIMS will be administered. Benztropine (up to 4 mg/day) is not to be administered 12 hours prior to rating scales. Benzodiazepines (up to

Protocol 31-14-204

3 mg/day lorazepam equivalents) are not to be administered 4 hours prior to rating scales.

- 5) A complete physical examination will be performed.
- 6) Height, body weight, and waist circumference will be measured.
- 7) Vital sign measurements (systolic and diastolic blood pressure and heart rate) will be recorded. Orthostatic assessments of blood pressure and heart rate will be made after the subject has been sitting for at least 5 minutes and again after the subject has been standing for approximately 2 minutes, but not more than 3 minutes.
- 8) A standard 12-lead ECG will be performed at rest after the subject has been lying down for approximately 5 minutes.
- 9) Fasting blood samples will be collected for clinical laboratory tests (hematology and serum chemistry, including TSH, glycosylated hemoglobin, and prolactin levels; prolactin samples to remain blinded). If the observed TSH level is outside the normal range, a test of T3 and T4 levels will be performed.
- 10) Urine will be collected for urinalysis and may be collected for a urine screen(s) for drugs of abuse (can be conducted at any time during the trial at the investigator's discretion).
- 11) A urine pregnancy test will be done on all FOCBP.
- 12) For all FOCBP and sexually active males, documentation of birth control methods will be completed.
- 13) AEs and concomitant medications will be recorded.
- 14) Drug accountability will be assessed.

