Subjects entering the double-blind randomized withdrawal phase will be randomized 1:1:1 to the half-dose arm, full-dose arm, or placebo arm. Doses in the aripiprazole arms will be based on the subject's stabilized dose during the single-blind stabilization phase. Subjects will be monitored for relapse during the double-blind randomized withdrawal phase. Relapse is defined as a loss of $\geq 50\%$ of the improvement experienced during the open-label stabilization phase (ie, improvement at the last assessment of YGTSS before randomization) on the YGTSS TTS. If a subject meets relapse criteria, they should be discontinued and treated according to the schedule of assessments.

There will also be a safety follow-up period (30 + 3 days) after the last dose of IMP or after the clinical site is notified that the subject prematurely discontinued their IMP.

During the pretreatment phase, modifications to a subject's pre-existing treatment are not to be made for the explicit purpose of entering this trial, but should be done only where deemed clinically appropriate by the investigator. Tapering rates for washout of medications are at the discretion of the investigator and are to be determined on an

Protocol 31-14-204

individual basis, with consideration to the subject's clinical condition, dose, and known pharmacokinetics (PK) of the medication being tapered, as long as the protocol-mandated discontinuation timeframe is met. The exception is a long-acting depot medication, which cannot be tapered and would be discontinued after the informed consent/assent is obtained.

[figure not shown]

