3.8.3.2 Treatment Discontinuation

After randomization, a subject may stop treatment permanently for a variety of reasons. Treatment discontinuations may be initiated by a subject who is not satisfied with treatment or may become medically necessary due to AEs, required treatment with a disallowed medication or therapy, or other issues, as determined by the investigator. However, each investigator must comprehensively review the circumstances and offer the subject options for continued treatment to the degree possible as described in [Section 3.8.3.5](#).

Protocol 31-14-204

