7.3 Handling of Missing Data

The primary endpoint is time from randomization to relapse during the double-blind randomized withdrawal phase. Subjects who complete or discontinue from the randomization phase without relapses will be considered as non-informative censoring in the primary analysis of the primary endpoint. Non-informative censoring means the dropout reason for subject who drops out of the trial without relapse is unrelated to efficacy. However, as the possibility of potential informative censoring in the randomized phase cannot be ruled out, sensitivity analyses of the primary endpoint will be performed under the assumption of informative censoring. Details of such sensitivity analyses will be provided in the statistical analysis plan (SAP).

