8.1 Primary Efficacy Endpoint

8.1.1 Primary Endpoint Analysis

The primary endpoint is time from randomization to relapse during the double-blind randomized withdrawal phase. Relapse is defined as a loss of $\geq 50\%$ of the improvement experienced during the open-label stabilization phase (i.e., improvement at the last

assessment of YGTSS before randomization) on the YGTSS TTS. Since this trial has terminated early due to withdrawal of postmarketing commitment (PMC), only relapse rate will be provided by treatment group for ITT sample.

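### A subject medicated before the exit YGTSS cannot be counted as a relapse, and the SAP neither classifies such exits nor contains the promised informative-censoring analyses

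*Protocol*

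**What the plan says.** Protocol 3.1 and SAP 8.1.1 define relapse as losing at least half of the open-label improvement on the YGTSS TTS. Neither makes new medication, or stopping because of worsening tics, an event.

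Protocol 3.7.1.8 covers early exit from the double-blind phase. It first asks sites to rate before a new psychotropic is started: "attempts should be made to complete ALL evaluations, particularly efficacy assessments (YGTSS, CGI, etc.), for the Week 12/ET visit prior to the administration". It then says that "if the subject receives a new psychotropic medication prior to ET procedures, no efficacy assessments should be done". Protocol 3.8.3.2 expects some subjects to stop because they are dissatisfied or because of "required treatment with a disallowed medication or therapy, or other issues, as determined by the investigator".

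Protocol 7.3 states: "Subjects who complete or discontinue from the randomization phase without relapses will be considered as non-informative censoring in the primary analysis". It explains non-informative as a dropout reason unrelated to efficacy, concedes that informative censoring cannot be ruled out, and defers the remedy: "Details of such sensitivity analyses will be provided in the statistical analysis plan (SAP"). Protocol 7.4.1 repeats that promise.

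SAP 8.1.1 says that, because the trial ended early, "only relapse rate will be provided by treatment group for ITT sample". SAP 5.3 imputes nothing. SAP 14 explains that the interim analysis was dropped and that efficacy is descriptive. It does not mention the censoring analyses.

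**The concern.** The trial exists to count loss of response after withdrawal. A subject whose tics return between visits and who receives another drug before being rated has plausibly lost response, yet no rating exists that could show it. Calling that exit unrelated to efficacy does not fit the subject. A Kaplan-Meier or Cox analysis does not recover the event, because it is never recorded and the subject simply leaves the risk set.

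In the SAP the question becomes how such a subject enters the relapse rate: in the denominator as not relapsed, left out, or counted as relapsed. The SAP does not say. The analysis that would have shown how much the choice matters was promised and is absent.

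**Working it through.** **1. The plan's own figures (Protocol 7.1): 38 per arm, relapse 65% on placebo and 34% on each active arm.**
- Total events: 38 × 0.65 + 2 × 38 × 0.34 = 24.70 + 25.84 = 50.54, stated as 51.
- Hazard ratio: ln(0.66)/ln(0.35) = 0.4155/1.0498 = 0.396, stated as 0.4.
- Events per comparison: D = 38 × (0.65 + 0.34) = 37.62.
- Schoenfeld power, Φ(√(D/4) × |ln HR| − z): 80.2% at HR 0.4 and two-sided 0.05; 79.9% at HR 0.396 and the final-look 0.045.

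The stated 51 events and about 80% power reproduce.

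**2. The path of one subject.** No qualifying YGTSS so far; worsens between visits; new psychotropic started; exit visit without YGTSS. Under the relapse definition there is no event. Under Protocol 7.3 the subject is censored as non-informative. Under SAP 8.1.1 no rule applies.

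**3. Illustration on the planned design.** Let f be the share of true relapses lost this way. The documents give no value, so every f below is an assumption. The observed proportion is (1 − f) × p, the hazard ratio becomes 0.396 × (1 − f_active)/(1 − f_placebo), and D = 38 × [(1 − f_placebo) × 0.65 + (1 − f_active) × 0.34].

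| f placebo / active | Relapsed/N placebo vs active | Difference (points) | HR | Power at 0.045 |
|---|---|---|---|---|
| 0 / 0 | 65.0% vs 34.0% | 31.0 | 0.396 | 79.9% |
| 5% / 5% | 61.8% vs 32.3% | 29.5 | 0.396 | 78% |
| 10% / 10% | 58.5% vs 30.6% | 27.9 | 0.396 | 75.6% |
| 20% / 10% | 52.0% vs 30.6% | 21.4 | 0.445 | 60% |
| 30% / 10% | 45.5% vs 30.6% | 14.9 | 0.51 | 43% |
| 10% / 20% | 58.5% vs 27.2% | 31.3 | 0.35 | 84% |
| 0 / 20% | 65.0% vs 27.2% | 37.8 | 0.317 | 92% |

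A log-rank simulation (3,000 runs, two-sided 0.05) agrees: 80.3% with no loss and 51.1% with 20% lost on placebo only, against 81.1% and 52.1% by formula.

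**4. Effect of the missing denominator rule, taking 20% / 10%.**
- Unrated exits counted as not relapsed: 52.0% vs 30.6%.
- Unrated exits left out: 0.52/(1 − 0.2 × 0.65) = 0.52/0.87 = 59.8%, and 0.306/(1 − 0.1 × 0.34) = 0.306/0.966 = 31.7%.
- Kaplan-Meier with censoring: 1 − 0.35^0.8 = 56.8%, and 1 − 0.66^0.9 = 31.2%.
- All counted as relapsed: 65.0% vs 34.0%.

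On placebo the same data give anything from 52% to 65%, depending on an unstated rule.

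**5. Per subject.** At the planned size one subject is 1/38 = 2.6 points. In a smaller arm it is more. The number randomized before termination is not in the documents.

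**The case against.** The other side has several good points.

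- **The trial was stopped.** No log-rank test, Cox model or interim analysis remains, so the hazard ratios and power values above describe an analysis that will not be run. This stands. Early termination explains dropping inference. It does not explain leaving undefined how the one reported figure is counted.
- **Sites are told to rate first, and YGTSS is scheduled at Weeks 1, 2, 3, 4, 6, 8, 10 and 12.** This stands and narrows the point: a relapse rated at an earlier visit still counts. What remains is the subject who worsens in a one- to two-week gap and is medicated before a rating. The request to rate first is only to attempt it, and the next sentence governs when the attempt fails.
- **Other outputs would give a hint.** The SAP tabulates discontinuation reasons (CT-2.2), concomitant medications (CT-4.2.3) and deviations, and lists relapse and YGTSS data (EFF-1, EFF-2.1). A reader might infer that nothing planned could reveal the problem; that goes too far. What is missing is the cross-classification with whether an exit YGTSS exists.
- **Counting every new psychotropic as relapse would misclassify.** Protocol 4.1 covers benzodiazepines for extrapyramidal symptoms. A subject so treated and not rated at exit may have had no return of tics. This stands, and the fix below is limited accordingly.
- **Exit reasons may not identify worsening.** The examples in Protocol 3.8.3.3 include meeting relapse criteria but no lack-of-efficacy category short of that. This stands as a cost.

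**Conclusion.** The gap is real and worth closing, at modest weight. A stated rule can prevent the primary event from being recorded, the protocol's assumption about such exits does not fit them, and the promised check is missing without explanation. The consequence now is a possibly misstated relapse rate in each arm.

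Three stronger readings are tempting and are not supported:

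- That failures are scored as successes. In the protocol's analysis they are censored, not counted as relapse-free to Week 12. In the SAP, not relapsed is only the default inference, because no rule is written.
- That the loss falls mainly on placebo and dilutes the effect. The documents give no figure by arm. With more loss on active the hazard ratio moves the other way (0.35 at 10% / 20%).
- That power drops to some particular value. The loss shares are assumed, small equal shares hardly matter (78% against 79.9% at 5% / 5%), and no test will be run.

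The conclusion rests on at least one subject having left in this way, which the documents cannot show.

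**What to change.** Keep the YGTSS definition as primary. In SAP 8.1.1, CT-5.1 and EFF-1:

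1. State the denominator of the relapse rate and how a subject who exits without a qualifying YGTSS is counted.
2. Add one sensitivity row. It counts as relapsed, on the medication start or exit date, any subject who leaves without an exit YGTSS and either started a medication recorded as given for tics or has a recorded exit reason of worsening tics or lack of efficacy. Medication given for another documented indication, such as extrapyramidal symptoms, does not count.
3. Add a by-arm count of non-relapse exits by reason and by whether an exit YGTSS exists.
4. In SAP 14, say what became of the sensitivity analyses promised in Protocol 7.3 and 7.4.1.

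The cost is some SAP wording, one row and one small table. Concomitant and psychotropic medications are already recorded at every double-blind visit and at follow-up. Some indications or exit reasons may need a blinded review of existing records. Some reclassified exits may not have met the YGTSS threshold, which is why this is a sensitivity row and not the primary count.

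The rule on rating after new medication belongs to the clinical team. Protocol 3.7.1.6.2 ties it to antipsychotics in the open-label phase, and 3.7.1.8 to psychotropics in the double-blind phase; the two should be reconciled.

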3.7.1.9 Post-treatment Follow-up Period

All subjects (completers and subjects who receive at least 1 dose of IMP and discontinue the trial for any reason) will be followed up for safety reasons 30 days (+ 3 days) after the last trial visit. Follow-up will consist of telephone contact to assess any AEs experienced since the last trial visit and information on ongoing AEs and serious TEAEs and recording of concomitant medications, including current psychotropic therapy.

3.7.2 Efficacy Assessments

3.7.2.1 Yale Global Tic Severity Scale

The YGTSS¹ is a semi-structured clinical interview designed to measure current tic severity. This scale consists of a tic inventory, with 5 separate rating scales to rate the severity of symptoms, and an impairment ranking. Ratings are made along 5 different dimensions on a scale of 0 to 5 for motor and vocal tics, each including number, frequency, intensity, complexity, and interference. Summation of these scores (ie, 0-50)

Protocol 31-14-204

provides a TTS that will be the primary outcome measure. The YGTSS ranking of impairment, with a maximum of 50 points, is based on the impact of the tic disorder on areas of self-esteem, family life, social acceptance, and school scores. This is a fully validated scale in adults and has become a standard instrument for the evaluation of the severity of TD in children.

3.7.2.2 Clinical Global Impression Scale for Tourette's Syndrome

The severity of illness and efficacy of IMP for each subject will be rated using the CGI-TS scale.¹⁴ To assess CGI-TS severity, the rater or investigator will answer the following question: "Considering your total clinical experience with this particular population, how mentally ill is the patient at this time?" However, the evaluation of illness will be limited to manifestations of TD only. Response choices include: 0 = not assessed; 1 = normal, not at all ill; 2 = borderline mentally ill; 3 = mildly ill; 4 = moderately ill; 5 = markedly ill; 6 = severely ill; and 7 = among the most extremely ill patients.

The rater or investigator will rate the subject's total improvement whether or not it is due to drug treatment. All responses will be compared to the subject's condition at baseline (Day 1). Response choices include: 0 = not assessed, 1 = very much improved, 2 = much improved, 3 = minimally improved, 4 = no change, 5 = minimally worse, 6 = much worse, and 7 = very much worse.

3.7.3 Safety Assessments

3.7.3.1 Adverse Events

Refer to [Section 5](#), Reporting of Adverse Events.

3.7.3.2 Clinical Laboratory Assessments

A central laboratory designated by the sponsor will be used for all laboratory testing required during the trial. The central laboratory should be used for all laboratory testing whenever possible (including unscheduled and follow-up labs, if needed). Reports from the central laboratory should be filed with the source documents for each subject. The central laboratory will provide laboratory results to the sponsor electronically.

Samples for serum chemistry, hematology, and urinalysis will be obtained at the visits designated in [Table 3.7-1](#) and [Table 3.7-2](#). Additional urine and blood samples may be collected for further evaluation of safety as warranted by the investigator's judgment. Subjects should be fasting for a minimum of 8 hours prior to any blood draws for all laboratory assessments. If nonfasting blood samples are obtained initially for determining

Protocol 31-14-204

eligibility for the trial, a fasting blood sample should be drawn at or prior to the baseline visit (prior to the first dose of open-label drug). Microsampling procedures may be used for obtaining blood samples for clinical laboratory analysis in order to minimize the amount of blood drawn from subjects. The laboratory tests to be evaluated in this trial are listed in [Table 3.7.3.2-1](#).

A urine pregnancy test will be performed at screening on all female subjects ≥ 12 years of age and all female subjects < 12 years of age if menstruation has started. Subjects with a positive result at screening will be excluded from the trial. In addition, urine and/or serum pregnancy tests can be performed at any point during the trial for female subjects ≥ 12 years of age and female subjects < 12 years of age if menstruation has started, if pregnancy is suspected. Any positive urine pregnancy test result will be confirmed by a serum pregnancy test. Treated subjects with a positive urine and serum pregnancy test must discontinue treatment, be withdrawn from the trial, and an immediately reportable event (IRE) form should be completed.

Any value outside the normal range will be flagged for the attention of the investigator who must indicate whether or not a flagged value is of clinical significance. If one or more values are questionable, the test(s) may be repeated. If the result of any test (or repeat test, if done) is indicated as clinically significant in the samples taken during the screening period, the subject will NOT be enrolled into the trial without the permission of the medical monitor. In addition, follow-up unscheduled laboratory tests should be performed for clinically significant abnormalities. Unscheduled laboratory tests may be repeated at any time at the discretion of the investigator for appropriate medical care.

Subjects will be excluded from the trial if they have any other abnormal laboratory test result at screening that, in the investigator's judgment, is medically significant in that it would impact the safety of the subject or the interpretation of the trial results. The following laboratory test results are exclusionary:

- 1) Platelets $\leq 75,000/\text{mm}^3$
- 2) Hemoglobin $\leq 9 \text{ g/dL}$
- 3) Neutrophils, absolute $\leq 1000/\text{mm}^3$
- 4) Aspartate aminotransferase (AST) $> 3 \times$ upper limit of normal (ULN) as defined by the central laboratory
- 5) Alanine aminotransferase (ALT) $> 3 \times$ ULN as defined by the central laboratory
- 6) Creatinine $\geq 2 \text{ mg/dL}$

Protocol 31-14-204

[Appendix 2](#) is included to assist investigators in their assessments of results that may be of potential clinical relevance, depending on the subject's medical history and clinical presentation.

Table 3.7.3.2-1 Clinical Laboratory Assessments	
Hematology: Hematocrit Hemoglobin Platelet count Red blood cell count White blood cell count with differential	Serum Chemistry: Alkaline phosphatase ALT AST Total bilirubin Blood urea nitrogen Calcium Chloride Cholesterol (total, low-density lipoprotein, and high-density lipoprotein) Creatinine Creatinine phosphokinase Gamma glutamyl transferase Glucose Glycosylated hemoglobin Lactate dehydrogenase Phosphorus, inorganic Potassium Total protein Sodium Triglycerides Uric acid
Urinalysis: Blood Glucose Ketones Microscopic exam (performed only if any part of the urinalysis is not negative) pH Protein Specific gravity	Additional Tests: Prolactin ^b Serum pregnancy, for confirmation of positive urine tests TSH ^a Urine drug (including alcohol) screen Urine pregnancy (FOCBP)

^aIf the observed TSH level is outside of the normal range, tests of triiodothyronine (T3) and thyroxine (T4) levels will be assessed.

^bThe blinded prolactin results will be reviewed by the designated unblinded medical monitor.

3.7.3.3 Physical Examination and Vital Signs

3.7.3.3.1 Physical Examination

A complete physical examination at the visits designated in [Table 3.7-1](#) and [Table 3.7-2](#). The principal investigator or his/her appointed designee is primarily responsible for performing the physical examination. If the appointed designee is to perform the physical examination, he/she must be permitted by local regulations and his/her name must be

Protocol 31-14-204

included on the US FDA Form 1572. Whenever possible, the same individual should perform all physical examinations. Any condition present at the post-treatment physical examination that was not present at the baseline examination should be documented as an AE and followed to a satisfactory conclusion. A complete physical examination is an integral part of study safety assessments and includes a urogenital assessment. A urogenital assessment should be performed on all trial subjects according to local medical standards as applied to other body systems. For the purposes of this trial, at a minimum, a screening urogenital exam is required, which could have been performed up to one calendar year prior to the date of the ICF being signed, or can be performed during the screening period. The urogenital examination may be performed by the subject's primary care provider or pediatrician as long as the source records are obtained and the findings documented. Post-baseline, medically relevant questions about the urogenital body system must be asked of the subject at all protocol-required physical exams, with answers documented accordingly in the source. The extent and scope of any part of the physical examination is to be left to the discretion of the investigator as deemed appropriate for each subject.

